The P01 application received a good impact score of 37 but was not recommended for funding by Council. In response to reviewer concerns, we initiated IRB00066136 to replicate the initial observations of oxytocin induced pain relief to a sustained heat stimulus. This was successful and the preliminary PK/PD model from the first study fit well the time course and degree of analgesia in this second study.

The P01 was extensively revised and resubmitted in January, 2021. This included revisions to each of the 6 proposed studies with IRB approval. The grant resubmission received an impact score of 20, was recommended by NIH Council for funding 3 months ago, and NIH Program in late November informed us that they anticipate requesting last minute documents in preparation for funding shortly.

This IRB application is for a revision to IRB00066130 (which has not been initiated) to estimate the IV oxytocin dose-response for analgesia to 5 min heating of the skin. We considered amending the approved protocol, but as noted in the table below, the study design was altered in so many fundamental ways in response to the NIH review that we felt a replacement was more appropriate.

Factor	IRB00066130	This study
Population	Healthy volunteers and those with advanced knee osteoarthritis	Healthy volunteers age 18-75, stratified by age
Sample size	20	24
Oxytocin dosing	Stepped 15 min infusions to target escalating plasma oxytocin concentrations	Constant rate 10 min infusions of placebo or 3 different oxytocin doses
Total oxytocin dose	41 mcg	1.3 or 7.3 mcg
Blinded	No	Yes
Blood sampling	Yes	No

Rationale for current application

Both preclinical and clinical evidence suggests that oxytocin may serve as a novel pain therapeutic and potential disease-modifying agent to prevent the transition from acute to chronic pain. This follows from observations that pain resolves quicker in women after cesarean delivery than other surgeries [1], and that hypersensitivity resolves quicker in rodents when neuropathic injury is performed after delivery, an effect blocked by inhibition of oxytocin action [2, 3]. Oxytocin may act peripherally to affect pain after injury. Since chronic pain is usually reduced acutely by peripheral nerve block, peripheral input is necessary, but most research assumes that input is normal and pain reflects ongoing central sensitization. We and others challenge

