This is a blinded, randomized, controlled study of IV infusion of placebo and 3 doses of oxytocin. In this study, healthy individuals will come to the Piedmont Plaza 2 Pain Clinical Research unit (CRU) or the CTSI CRU for a training visit and then to the CTSI CRU for two other study days, separated by at least 72 hr. During the training day they will report pain on a 0 (no pain) to 10 (worst imaginable pain) scale each minute during a 5 min heating of the skin of the lateral calf to a temperature (45°C) using an FDA approved, commercially available device (Medoc, TSA II). If pain score is less than 2 at the end of this stimulus, the test will be repeated with the probe set to 46°C. If pain score is less than 2 on that occasion, the test will be repeated with the probe set to 47°C. If pain score is less than 2 on that occasion the individual will not go on to further study and will be reimbursed for the training day only. On the other two visits, subjects will receive on one visit IV saline followed in one hour by IV oxytocin, 1.3 µg and on the other visit they will receive IV oxytocin, 0.3 µg followed in one hour by IV oxytocin, 7 µg. Infusions will be given over 10 minutes. The order of these two dosing regimens will be randomized and double blind, with solutions released from the research pharmacy. As a result, each subject will receive oxytocin doses of 0, 0.3, 1.3, and 7 µg in this double blind design. Pain report each minute and at the end of a 5-min heating will be recorded before the first infusion and then with the 5-min heat test ending at 15, 30, and 45 min after the ending of the infusion. The probe temperature used for heating will be that determined during the training day. Immediately after the 60 min pain report the second infusion will be given and pain intensity at the end of 5-min of heating recorded at 15, 30, and 45 min thereafter. The study will then end.

Phase II trials

Setting

The training visit will occur at either the Pain CRU at Piedmont Plaza 2 or the CTSI CRU. Drug study visits will occur on the main campus at CTSI CRU.

Subjects selection criteria

The study will enroll healthy subjects.

Inclusion Criteria

1. Male or female ≥ 18 and < 75 years of age, Body Mass Index (BMI) <40 .
2. Generally in good health as determined by the Principal Investigator based on prior medical history, American Society of Anesthesiologists physical status 1, 2, or 3
3. Fully vaccinated against COVID-19

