desaturation (< 90) will be treated with supplemental oxygen, nasal cannula, face mask, or non-rebreathing mask depending upon the degree desaturation and the response to therapy.

Outcome Measure(s)

Primary Outcome Measure

Name: Verbal pain score (0-10) at the end of 5 min of skin heating

Type: Primary

Time Frame: For 45 minutes after the end of each study drug infusion

Description: Pain scores are measured each minute during 5 min heating of the skin of the calf

Analytical Plan

The primary analysis will use NONMEM to create a dose response at the time of peak oxytocin effect on pain at the end of a 5 min noxious heat stimulus. To do so, pain scores over time will first be modeled using NONMEM with derived parameters of maximum effect (Emax), predicted concentrations from the PK/PD model to produce a 50% and 90% maximum drug effect (C50 and C90, respectively), the steepness of the dose response curve (γ), and the time to peak effect. Inter-subject variability (e.g., biological variability) will evaluate additive, proportional, and exponential models. Residual intrasubject variability (e.g., noise) will typically require an additive and multiplicative error model. The influence of covariates (e.g., age, sex, weight) on model parameters will be analyzed by serial inclusion / exclusion, with significance determined by the likelihood ratio test ($p < 0.01$ if the decrease in $-2 \log$ likelihood exceeds 6.6 ($\chi^2_{0.99}$, $df = 1$)). Parameters will be estimated using first-order conditional estimate with η - ε interaction.

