Covariate effects deemed significant by likelihood ratio test will be validated using jackknife cross-validation [10]. Jackknife cross-validation provides an estimate of the utility of the covariate to inform the pharmacodynamics in a future individual, rather than merely characterize the pharmacodynamics in the individuals from which the model was derived. The jackknife cross-validation divides the data into N subsets. Each subset leaves out a single individual. The parameters of the model are re-estimated for each subset with and without the covariate being validated. The inaccuracy (mean $((|measured - predicted|) / predicted)$), of the model with and without the covariate is measured in the excluded individual. The covariate is only being included in the final model if the improvement in model accuracy in the N iterations is significantly greater than 0. Jackknife cross-validation helps compensate for NONMEM's ability to identify very small covariate effects that do not meaningfully contribute to accuracy in future patients.

Expected outcomes. Based on pain ratings and an estimate of the PK/PD model from preliminary data (Fig 1), we anticipate that the maximum oxytocin effect is a 50-60% reduction in pain rating from the 5 min heat stimulus. We anticipate that the oxytocin dose range will demonstrate a sigmoidal dose-response with a peak within 10 min after the end of infusion and an ED80 of ~ 5 μ g. In a separate simulation of 7 μ g oxytocin without a prior injection of 0.3 μ g, the peak effect was within 1% of the same value, supporting this stepped dosing study design. The expected peak plasma oxytocin concentration after the 7 μ g infusion following the 0.3 μ g infusion is 400 pg/ml, below that which produced subjective symptoms in previous studies.

Human Subjects Protection

Subject Recruitment Methods

Healthy subjects will be recruited from our current database of volunteers BG05-468, word of mouth and Be Involved website; The research nurses; [name] and [name], LPN will conduct the recruitment of study subjects.

Potential subjects from the database will be contacted via phone or email, per their request. Potential subjects from the Be Involved website will be contacted according to the information they provide.

Informed Consent

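### With no oxytocin concentrations measured, a weight, sex or age difference in exposure may be misread as a pharmacodynamic difference in C50 or C90

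*Combined protocol and SAP*

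**What the plan says.** - **No concentrations are measured.** In the table comparing this study with the protocol it replaces (History of recent oxytocin research), the row "Blood sampling" reads Yes for the replaced protocol and No for this one.
- **Dosing is fixed.** Study Design states that "each subject will receive oxytocin doses of 0, 0.3, 1.3, and 7" µg, with no scaling to body size.
- **The concentration axis is carried over.** The Analytical Plan defines C50 and C90 as "predicted concentrations from the PK/PD model to produce a 50% and 90% maximum drug effect". The Rationale describes the source as a two-compartment NONMEM fit in 11 subjects. It does not say whether weight, sex or age enters that fit.
- **Covariates are then tested.** "The influence of covariates (e.g., age, sex, weight) on model parameters will be analyzed by serial inclusion / exclusion", at p < 0.01. C50 and C90 are among the parameters.
- **The result is described as pharmacodynamic.** The Sample Size section sizes the trial for the precision of pharmacodynamic parameters. The Analytical Plan says the jackknife assesses "the utility of the covariate to inform the pharmacodynamics in a future individual".

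Nowhere does the plan say how a difference in exposure will be told apart from a difference in sensitivity.

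**The concern.** Drug effect in this kind of model depends on concentration relative to C50. If two subjects are equally sensitive but one reaches lower concentrations after the same dose, a model that assigns both the same predicted concentration must give the one with lower exposure a higher C50. Pain scores alone cannot show that the cause was exposure.

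At stake is the interpretation of any covariate effect on C50 or C90, and the model refinement in Additional Objective 2. A refined model that places a kinetic effect on a sensitivity parameter would carry that misattribution into later dosing predictions and into later studies that use it.

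**Working it through.** **1. The plan's own figures.** With an Emax model, γ = 1 (Rationale) and ED50 = 1.3 µg (the dose predicted to give 50%):
- 0.3/(0.3 + 1.3) = 18.8%, 1.3/2.6 = 50% and 7/8.3 = 84.3%, against the stated 20%, 50% and 85%.
- ED80 = 1.3 × 0.8/0.2 = 5.2 µg, against the stated value of about 5.
- The 0.99 chi-square point on 1 df is 6.635, stated as 6.6.

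These agree. The sample size (21, raised to 24) cannot be reproduced, because the corrected confidence range is not defined and no variance or power is given. The only visible link to the 40% covariate effect is 2 × 20%.

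**2. Why exposure and C50 cannot be separated.** Let true concentration be k × C, where C is the predicted value. Then

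E = Emax (kC)^γ / [C50^γ + (kC)^γ] = Emax C^γ / [(C50/k)^γ + C^γ].

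The fit returns C50/k, with Emax and γ unchanged. The two forms are identical at every dose and time, so the four dose levels do not help. Nor do the heat tests ending at 15, 30 and 45 min after infusion, a period over which the plan itself predicts a fairly stable effect.

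**3. Size, by assumption.** Suppose clearance and volumes all scale as weight to the power b, so that k = (W/Wref)^(−b), and suppose the PK model omits weight. The apparent C50 ratio is then (W2/W1)^b. This is exact only if clearance and volumes scale alike. The documents give neither b nor subject weights; entry is limited only by BMI < 40.

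| Contrast | b = 0 | b = 0.5 | b = 0.75 | b = 1.0 |
|---|---|---|---|---|
| 100 v 60 kg | 1.00 | 1.29 | 1.47 | 1.67 |
| 85 v 70 kg | 1.00 | 1.10 | 1.16 | 1.21 |

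The Sample Size section treats an effect of about 40% as possibly clinically consequential. For 100 v 60 kg that needs b = ln 1.40 / ln 1.667 = 0.66 or more. For 85 v 70 kg it is not reached anywhere in this range.

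**4. How often the artefact would be flagged.** A simulation of 20,000 trials used 24 subjects, half of each sex, with no true pharmacodynamic covariate effect. Assumed median weights were 85 and 72 kg by sex, with log-SD 0.18. The between-subject SD of log C50 came from two readings of the plan's 20% at n = 21:
- total 95% CI width: (0.10/1.96) × √21 = 0.234;
- 95% CI half-width: (0.20/1.96) × √21 = 0.468.

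Share of trials passing the p < 0.01 likelihood ratio test, each covariate tested alone:

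| SD | Covariate | b = 0 | b = 0.5 | b = 0.75 | b = 1.0 |
|---|---|---|---|---|---|
| 0.234 | weight | 1.6% | 29% | 64% | 88% |
| 0.234 | sex | 1.5% | 5% | 8% | 13% |
| 0.468 | weight | 1.6% | 7% | 16% | 29% |
| 0.468 | sex | 1.4% | 2% | 4% | 5% |

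This treats each subject's C50 as observed, so it simplifies the NONMEM fit, and it stops before the jackknife.

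**5. The safeguards.** The likelihood ratio test asks whether a covariate improves fit. The jackknife asks whether it improves prediction of pain in the omitted subject. A covariate that acts purely through exposure can do both, so passing them does not show that it acts on sensitivity. Stratifying by weight balances numbers but gives no information on kinetics.

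**The case against.** Several points on the other side are sound.

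- **The documents do not say that the PK model lacks weight, or that oxytocin exposure depends on weight.** They are silent on both. A reader might infer that a false weight or sex effect will be reported; that does not follow. If the model carries weight, or exposure does not vary with it, the weight artefact is nil.
- **A reader might infer that Additional Objective 1 would be answered wrongly.** That objective concerns sex or age and oxytocin's effect; it names neither weight nor sensitivity. A difference in effect at a fixed dose, including any exposure part, is a valid answer.
- **A reader might infer that the primary result is compromised.** It is not. The primary analysis is a dose-response, expected results are given in µg, and a dose-scale effect is correct as the combined effect of exposure and sensitivity.
- **A false sex signal through weight is uncommon** under the assumptions above (2% to 13%), and a retained weight term could absorb it.
- **The preliminary model predicted the analgesic time course in a second study of 10 volunteers.** This supports its typical prediction, but does not show that it captures exposure differences by weight, sex or age.
- **The jackknife wording describes predictive usefulness,** which holds whether the covariate acts through exposure or sensitivity. It is loose wording more than a claim about sensitivity.

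What remains is the lack of identifiability. A separate PK protocol in healthy subjects is listed in the History section, but the Analytical Plan does not say that it will supply PK covariates.

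**Conclusion.** The concern holds as a limit on interpretation. Any weight, sex or age difference in exposure not already in the carried-over PK model may be misread as a difference in C50 or C90, and nothing in the plan can separate the two. The exposed conclusions are pharmacodynamic statements about C50/C90 and the refined model of Additional Objective 2.

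The size depends on assumptions that the documents neither supply nor rule out. It runs from nothing to 1.67 fold for a wide weight contrast, and to 1.21 fold for a modest one. It reaches the plan's 40% mark only with a wide contrast and a fairly steep exponent. Whether it would be declared significant depends equally on the between-subject SD, which the plan does not give. The change should be made, because it alters what the trial may conclude about C50 and the refined model.

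**What to change.** Amend the Analytical Plan as follows.

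1. Report age, sex and weight effects on ED50 (µg) and Emax, described as combined effects of exposure and sensitivity.
2. State the PK model used to predict concentrations and which covariates, if any, it carries.
3. Describe a C50 or C90 covariate effect as pharmacodynamic only if it persists when the model is refitted with weight scaling on clearance and volumes over a stated range of exponents, for example 0 to 1. Do not rely on one exponent estimated from the 11 subjects, three of whom had a 1 min infusion; it would probably be imprecise.
4. For sex and age, state that a residual exposure effect unrelated to weight cannot be excluded.

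For weight itself, item 3 is a strict test. An apparent exponent θ on C50 becomes θ − b after scaling at b, so any θ between 0 and 1 could be explained by exposure alone and would not qualify.

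The cost is a few extra model runs and a narrower conclusion on C50. No blood sampling and no change to visits, doses or sample size is needed.

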The projected sample size is 24 subjects. Our current estimates indicate that the confidence interval for studies of 21 individuals with pain intensity ratings will determine the pharmacodynamic parameters with a corrected confidence range < 20%. A corrected confidence range < 20% implies that mixed effect analysis will distinguish covariate effects in the range of 40% in a study with 21 or more subjects. This is the range at which the covariate effect may be clinically consequential. In practice, mixed-effects analysis with NONMEM is often sensitive to covariate effects smaller than predicted by preliminary analyses. The sample size is increased to 24 to provide stratification by age (3 strata), weight (2 strata), and sex. The crossover design permits accurate determination of dose linearity despite expected high inter-subject variability in pain ratings.

Interventions and Interactions

At all study visits temperature will be measured and participants queried regarding recent history of symptoms commonly associated with COVID-19 or recent close contacts with anyone with a positive COVID-19 test.

Study Visit 1:

The participant will report to the Pain CRU or the Wake Forest CTSI CRU. The participant will review and sign the Informed Consent. After informed consent is adequately

obtained, a detailed medical history will be obtained from the participant, female participants will have a urine pregnancy test performed to determine pregnancy status. Vital signs to include blood pressure (BP), heart rate (HR), respiratory rate (Resp) and oxyhemoglobin saturation by pulse oximetry (POX) will be measured and recorded along with height and weight.

Once eligibility has been determined the participant will be trained in study procedures. This will include pain ratings to brief (5 sec) heat stimuli on the lateral calf to 39, 41, 43, 45, 47, and 49°C and then a pain intensity rating each minute for 5 mins during heating to 45°C. If the pain report to 45°C is < 2 at the end of the 5 min, a second trial using 46°C will be done, and if that also results in pain intensity < 2, a third trial with 47°C will be performed. Subjects who have pain intensity < 1 with the 47°C 5-min stimulus will not be further studied. The duration for visit 2 will be approximately 2 hours

Study Visit 2

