On the second visit, the participant will report to the CTSI CRU. Baseline vital signs (BP, HR, Resp, POX) will be obtained for a baseline measurement, a catheter inserted into a peripheral vein in the upper extremity and pain report to 5 min heating of skin on the calf at the temperature determined in Visit 1 will be recorded. Subjects will then receive two 10 min infusion of study drug, with infusions separated by 60 min and 5 min heat pain testing performed with each 5 min test ending at 15, 30, and 45 min after the end of each infusion. Subjects will be randomized to receive either 1) IV infusion of saline followed by oxytocin, 1.3 µg or 2) IV infusion of oxytocin 0.3 µg followed by oxytocin 7 µg. Which of these regimens is administered on study visit 2 will be randomized and double blind, with study drugs provided by the research pharmacy. The intravenous catheter will be removed after all data collection and the subject discharged from the CRU. The duration for study visit 2 will be approximately 4 hours.

Study Visit 3

On the third visit, the participant will report to the CRU and all procedures performed as in study visit 2. The pair of IV infusions will be the alternate to that used in study visit 2. The duration for study visit 3 will be approximately 4 hours.

Safety and Monitoring:

Assessment of Side Effects: Significant side effects are defined as changes > 30% from baseline in the mean arterial pressure, HR, or oxyhemoglobin pulse oximetry < 90. Any unexpected or serious side effects will be reported to the IRB within 24 hrs. Peripheral oxyhemoglobin saturation, BP and HR will be measured non-invasively before and 15, 30, and 60 min after each IV infusion. If either BP or HR change by > 30%, or oxyhemoglobin saturation decreases to less than 90, and require treatment, these vital signs will be repeated at 5-minute intervals until vital signs are stabilized.

Treatment of Side Effects: Mean blood pressure elevations greater than 30% of baseline will be treated with labetalol 5-15 mg IV incrementally until BP elevation is less than 30% elevated. Reductions in mean BP > 30% of baseline will be treated with incremental ephedrine 5-20 mg, IV. Heart rate (HR) reductions or elevations > 30% of baseline will be treated with incremental glycopyrrolate 0.2 mg IV or propranolol 0.2 mg IV, respectively. Peripheral oxyhemoglobin

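### The NONMEM model has no between-visit term although the dose pairs fall on different days; if ratings shift between days, precision is lost and standard errors may be misstated

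*Combined protocol and SAP*

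**What the plan says.** The Analytical Plan names two levels of variability. The first is between subjects: "Inter-subject variability (e.g., biological variability) will evaluate additive, proportional, and exponential models". The second is within subjects: "Residual intrasubject variability (e.g., noise) will typically require an additive and multiplicative error model". It names no visit, occasion, period or sequence term. The parameters it lists are Emax, C50, C90, γ and time to peak effect; no baseline parameter is among them.

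Under STUDY DESIGN, dosing takes place on "two other study days, separated by at least 72 hr". One day carries saline then 1.3 µg, the other 0.3 µg then 7 µg, and "The order of these two dosing regimens will be randomized and double blind".

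Each dosing day starts with a pre-infusion test. Under Study Visit 2, "pain report to 5 min heating of skin on the calf at the temperature determined in Visit 1 will be recorded". Under Study Visit 3, "On the third visit, the participant will report to the CRU and all procedures performed as in study visit 2". Three heat tests follow each infusion. The plan does not say how the two pre-infusion tests enter the model, which parameters carry subject effects, whether those effects are correlated, or how standard errors are computed.

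**The concern.** A crossover removes differences between subjects. It does not remove differences between days when doses are tied to days in pairs. A shift in a subject's rating level on one day is shared by every test of that day. With only subject and residual terms, the model treats that shared shift as independent noise.

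The placebo and the top dose are never given on the same day, so the 7 v 0 µg comparison, which largely fixes the height of the curve, takes the full day-to-day shift. The pre-infusion test on the 0.3/7 µg day is a same-day, drug-free reference that could correct for it, and the plan gives it no role. Two things are at stake: precision in the dose-response estimates, and whether the reported uncertainty is right.

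**Working it through.** **No plan figure to reproduce.** The Sample Size section says that 21 subjects "will determine the pharmacodynamic parameters with a corrected confidence range < 20"%, and then "The projected sample size is 24 subjects". It gives no SD, confidence level or formula, so this cannot be re-derived, and nothing below relies on it beyond n = 24.

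**Inputs from the documents.** 24 subjects; two dosing visits; per visit one pre-infusion test and three tests after each of two infusions, so 7 per visit and 14 per subject. STUDY DESIGN also mentions a pain report at 60 min that is not in the list of test times; it is not counted.

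**Assumed, because the documents give no values.** Residual SD σ = 1 pain point, subject SD 2, visit SD τ from 0 to 1.0. The pre-infusion mean equals the saline mean; the other doses have free means. The subject SD cancels from every contrast below.

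**7 v 0 µg without a visit term.** The estimate is the mean of three tests at 7 µg minus the mean of five drug-free tests (four on the saline day, one on the 7 µg day). The net weight on each day's shift is 1 − 1/5 = 4/5 on one day and −4/5 on the other.
- True variance = [σ²(1/3 + 1/5) + 2τ²(4/5)²]/24 = [0.533 + 1.28τ²]/24.
- The best-fitting residual variance is s² = σ² + τ²(14 − 7)/13 = 1 + 0.538τ². The 7 is 2 × 7²/14, the part taken up by the subject effect.
- Reported variance = 0.533 s²/24.

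**7 v 0 µg with a visit term and the pre-infusion tests.** Put weight w on the saline-day drug-free mean and 1 − w on the same-day pre-infusion test. The variance is [1/3 + w²/4 + (1 − w)² + 2τ²w²]/24. It is smallest at w = 1/(1.25 + 2τ²), where it equals [4/3 − w]/24.

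| Visit SD | Reported SE, no visit term | True SE, no visit term | Understated by | True SE with visit term | True SE cut by |
|---|---|---|---|---|---|
| 0 | 0.149 | 0.149 | 0% | 0.149 | 0% |
| 0.25 | 0.152 | 0.160 | 5% | 0.159 | 0.6% |
| 0.5 | 0.159 | 0.189 | 16% | 0.178 | 6% |
| 1.0 | 0.185 | 0.275 | 33% | 0.207 | 25% |

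At visit SD 0.5, for example: true √[(0.533 + 0.320)/24] = 0.189; reported √[0.533 × 1.135/24] = 0.159; with the visit term w = 0.571 and √[0.762/24] = 0.178. The 0.3 v 0 µg contrast has the same values.

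**Other contrasts, reported/true SE at visit SD 0.25, 0.5, 1.0.**
- 7 v 1.3 µg (across visits): √[0.667s²/(0.667 + 2τ²)] = 0.93, 0.81, 0.62.
- 1.3 v 0 µg (within a visit): √[0.533s²/(0.533 + 0.08τ²)] = 1.01, 1.05, 1.16.
- 7 v 0.3 µg (within a visit): √s² = 1.02, 1.07, 1.24.

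**Both parts are needed.** If the pre-infusion tests are left out, 7 v 0 µg rests on three tests against three, with variance [2/3 + 2τ²]/24 whether or not a visit term is fitted. The term then corrects the SE but gains no precision.

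**Planned parameters.** A linearised Emax model in dose was checked (baseline 5, Emax 0.55, C50 at 1.3 µg, γ = 1; assumed subject SDs 2 on baseline, 0.15 on Emax, 0.5 on log C50).
- γ estimated, uncorrelated subject effects: reported/true SE for Emax, C50 and γ is 0.89–0.91, 0.72–0.76 and 0.52–0.56 at visit SD 0.25, 0.5 and 1.0. Extra variance from omitting the visit term is 2%, 16–18% and 94–102%.
- γ estimated, correlated subject effects on all four parameters (subject SD 0.3 on γ): reported/true SE is 1.00 throughout; the extra variance stays at about 2%, 17% and 100%.
- γ fixed: reported/true SE is 0.97–1.05; extra variance is at most 8% at SD 0.5 and 43% at SD 1.0.

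These are linear approximations, not NONMEM runs.

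**The case against.** **The size is unknown.** Every effect above needs a non-zero between-visit variance, and the documents give none. At visit SD 0.25 the consequences are small. This stands.

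**The SE error depends on unstated choices.** With a full correlated set of subject effects, or with robust (sandwich) standard errors, the reported SEs can be right without a visit term. A reader might infer that the planned model is bound to give wrong error bars; the text does not support that. The precision loss survives, because neither choice recovers it.

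**No pairwise tests are planned.** A reader might turn the 16% and 33% into a nominal 5% test with 10% or 19% error for 7 v 0 µg. The arithmetic is right (ratios 0.84 and 0.67 against 1.96), but the plan estimates curve parameters and its only named test is the likelihood ratio test for covariates. Those error rates describe no analysis in the plan.

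**The baseline may absorb the shift.** The expected outcomes are worded as a percentage reduction in pain. If that means relative to the same day's pre-infusion test, much of a day shift drops out. But one test's error is then shared by all six later tests of that day. For simple differences the true variance for 7 v 0 µg is [2/3 + 2]/24, an SE of 0.333 at any visit SD, larger than the 0.275 above. A subject-plus-residual model would report √[0.667 × (1 + 6/11)/24] = 0.207, which is 38% too small. Subtraction does not replace the visit term.

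**The wording is open.** The phrase on residual error describes model building and does not forbid an occasion term. True, but no listed option is one.

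**More parameters from 24 subjects.** The stability of the larger fit was not examined. This is a real, small cost.

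**Conclusion.** The point holds as a conditional one. The plan names no between-visit term, three of the five contrasts examined cross visits, and the pre-infusion tests that would inform such a term are collected but given no stated use.

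The loss of precision is the firmer half. With residual SD 1, omitting the term and the pre-infusion tests' day-specific information costs nothing at visit SD 0, under 1% of the SE for 7 v 0 µg at 0.25, about 6% at 0.5 and 25% at 1.0. The misstatement of SEs is the weaker half. In the dose-mean model it is 0%, 5%, 16% and 33% for 7 v 0 µg, and it runs the other way for the two within-visit contrasts. For Emax, C50 and γ it ranges from none to about half the true SE at visit SD 1.0, depending on the random-effect structure and SE type, which the plan does not state.

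It would go too far to say that the error bars are wrong or that precision is lost. Without a between-visit SD, the documents support only that both may happen.

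**What to change.** In the Analytical Plan:
- Enter the pre-infusion heat test of each dosing visit as an observation in the NONMEM model, with a baseline pain parameter.
- Add an inter-occasion (visit) random effect on baseline pain, besides the subject effect.
- Optionally add visit number (2 or 3) as a fixed effect on baseline. Order is randomized, so this is a refinement; its gain was not calculated.
- State which parameters carry subject effects, whether these are correlated, and whether standard errors are model-based or robust.

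No subject, test or procedure is added. The cost is one or two more parameters to estimate from 24 subjects. If the visit variance is estimated at zero and the optional fixed effect is not used, the model reduces to one with subject and residual terms only, as now stated.
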